4. AIM

The aim of the RCT is to evaluate the effect of needle tenotomy when treating impending ulcers associated with hammer, mallet and claw toe deformities.

The study is designed as a prospective RCT comparing needle tenotomy with conservative treatment, for patients with deformities and impending ulcers associated with the three deformities. Primary endpoint will be number of new ulcers incurred, defined as ulcers associated with hammer, mallet and claw toe deformities, placed on treated foot.

Secondary endpoints will be complications: infections (defined as ailment associated with procedure or ulcer, that is diagnosed as infection by attending health professional), transfer lesions (defined as impending ulcers or actual ulcers at anatomical sites associated with hammer, mallet and claw toes in patients with diabetes, on non-treated hammer, mallet and claw toes after surgical treatment), minor amputations (defined as amputations below ankle level), major amputations (defined as amputations at or above ankle level).

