5.4 Visit-plan

Patients in both the intervention and conservative groups will be expected to adhere to a specified visit-plan

Visit-plan Study IV	Inclusion	Day 0	Day 7	Day 14	End ¹	Follow-
						up ²
	0.1	a a b b	a	a a a i	2.0	2 0
Duration	3 hours	30 min	30 min	30 min	30	30 min
					min	
In/exclusion criteria	+					
Baseline blood samples and physical	+					
exam						
Patient history	+					
Foot Examination	+	+	+	+	+	+
Changes in Medicine/ new ailments			+	+	+	+
Toe systolic blood pressure (TSB)	+					
Ankle/brachial pressure index (ABPI)						
Neurological assessment	+					
Randomization	+					
Tenotomy/silicone spacer application ³		+				
Standard Care & offloading	+	+	+	+	+	+
Footwear assessment		$+^{4}$	+	+	+	+

1: This visit only happens if patient incurs on of the named endpoints

2: Follow-up visits are performed at 3, 6 and 12 months

- 3: Depending on allocated treatment
- 4: All Patients receive therapeutic sandals with individualized insole

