5.5.1 Inclusion

Inclusion visit can only take place when written consent form is signed by patient, and filed in patient log.

The following procedures will be performed:

- In/exclusion criteria (see section 5.2)
- Baseline blood samples including:
 - o Hemoglobin A₁C
 - o Creatinine
 - o Estimated glomerular filtration rate
 - o Hemoglobin
 - o Albumin
 - o International normalized ratio
 - Low-density lipoproteins
 - o Leucocytes
 - o C-reactive protein
 - All blood samples are analyzed immediately, and nothing is preserved in biobank.
 The total amount of blood is evaluated to be less than 50ml pr. patient.
- Baseline physical examination including measurements of:
 - o Blood pressure
 - o Heart rate
 - Oxygen Saturation
 - o Heart and pulmonary auscultation
 - o Electro Cardiogram

- o Height
- o Weight
- Patient history including information on:
 - o Gender
 - male or female
 - o Diabetes type
 - 1 or 2
 - Duration of diabetes
 - measured in years with no decimal
 - o Duration of foot ulcer
 - measured in days
 - Competing diseases/comorbidity (ASA group is also registered)
 - By diagnosis and year of debut
 - o Current medicine
 - quantity and type
 - \circ Smoking
 - quantity and nature, present or past
 - Alcohol intake
 - quantity
 - Height, weight and BMI
 - In m(two decimals), kg(one decimal) and kg/m²(one decimal)
 - o Prior surgery on feet
 - Type and year
 - Prior ulcers of feet/legs
 - Location and year
 - Prior amputations
 - Location, type and year
 - o Prior/current history of Charcot's ailment
 - Debut year
 - Activity
 - Retinopathy
 - Simplex, proliferative and/or laser treated

- o Urinary albumin excretion rate
 - Normal, micro-, macro- or prior albuminuria
- Peripheral neuropathy
 - Yes/no
 - Pain associated with?
- Prior offloading therapy
 - Type
- o Relationship status
 - Married yes/no and/or living with partner yes/no
- Foot examination
 - Inspection of pressure point, and deformities
 - o Pulses
 - Deformities
- TSBP and ABPI
 - o TSBP and ABPI are performed by educated staff and results evaluated
 - Patients with TSB under 30 mmHg are referred to department of vascular surgery where deemed necessary
- Neurological assessment
 - o Biothesiometry tests are performed by educated staff
 - Monofilament testing is performed by educated staff
 - Neuropathy symptoms are examined and registered
- Randomization
 - o Randomization is performed in RedCAP
- Impending ulcer evaluation
 - Anatomical placement

5.5.2 Visit Day 0

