- Foot examination
 - Inspection of pressure point, and deformities
 - o Pulses
 - o Deformities
 - o New Ulcers

- Standard care & offloading
 - See section 5.3.2
- Tenotomy/conservative treatment application
 - The allocated treatment is performed
 - For details on tenotomy see section 5.3.1
 - For details on conservative treatment see section 5.3.2
- Impending ulcer evaluation
 - Anatomical placement
- Ulcer evaluation (if ulcer incurred)
 - Assessment of ulcer surroundings
 - Assessment of infection
 - Assessment of healing
- Measurement of longest length, width and depth in mm
- Measurement of area in mm³(length*width*depth)
 - Assessment of incision site (where applicable)
 - o Measurement of length, width and depth of ulcer(s) after debridement
- Categorizing by Texas Grading System
- Footwear assessment
 - Footwear and/or current offloading is evaluated
 - All patients in conservative and treatment group will be offered therapeutic sandals with customized insole at this visit
- Changes in medicine/new ailments
 - o Changes to the patient's medicine, and/or new diagnosis are registered

5.5.3 Visit Day 7, 14

The following is a specification of the above mentioned visits. If at any visit, before week 10, the impending ulcer has been deemed as progressed to active ulcer, patient is planned for end visit. If Patient incurs ulcer between visit day 14 and 3 month visit, patient contacts study personal to arrange end visit as soon as possible.

• Foot examination

- Inspection of pressure point, and deformities
- o Pulses
- o Deformities
- New Ulcers (not associated to registered impending ulcers)
- Changes in medicine/new ailments
 - o Changes to the patient's medicine, and/or new diagnosis are registered
- Standard care & offloading
 - See section 5.3.2
- Impending ulcer
 - Has impending ulcer progressed to active ulcer
- Ulcer evaluation (if relevant)
 - o Assessment of ulcer surroundings
 - o Assessment of infection
 - Assessment of healing
 - o Ulcer photo
 - o Measurement of longest length, width and depth in mm
 - Measurement of area in mm³(length*width*depth)
 - Assessment of incision site (where applicable)
 - o Measurement of length, width and depth of ulcer(s) after debridement
 - o Categorizing by Texas Grading System
- Footwear assessment
 - o Footwear and/or current offloading is evaluated
- Complications
 - Complications associated with tenotomy is registered (if relevant)
 - SAE is registered (if relevant)

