5.5.5 Follow up

The following is a specification follow up visits. Performed at 3, 6 and 12 months post day 0 visit

- Foot examination
 - Inspection of pressure point, and deformities
 - o Pulses
 - o Deformities
 - o New Ulcers
- Changes in medicine/new ailments

- o Changes to the patient's medicine, and/or new diagnosis are registered
- Standard care & offloading
 - See section 5.3.2
- Impending ulcer
 - Has impending ulcer progressed to active ulcer
- Ulcer evaluation (if relevant)
 - Assessment of ulcer surroundings
 - Assessment of infection
 - Assessment of healing
 - Ulcer photo
 - o Measurement of longest length, width and depth in mm
 - Measurement of area in mm³(length*width*depth)
 - Assessment of incision site (where applicable)
 - Measurement of length, width and depth of ulcer(s) after debridement
 - o Categorizing by Texas Grading System
 - Footwear assessment
 - \circ $\;$ Footwear and/or current offloading is evaluated
 - Complications
 - Complications associated with tenotomy is registered (if relevant)
 - o SAE is registered (if relevant

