5.8 Statistics

All statistical analysis will be performed using the version of SAS currently used at our institute. All data will be analyzed on the intention to treat basis. All baseline data will be presented using appropriate summarizing statistics. Appropriate comparable statistical analysis will be applied to

- Incidence of new ulcer(s) in treated limb
- Mean time (in days) to healing of incision sites
- Incidence of minor amputations
- Incidence of major amputations

Odds-ratio will be applied to

- The incidence of secondary infection
- Pain in treated limb, associated with tenotomy
- Transfer lesion

Sample-size

The calculation is done with a Type 1 error rate (α) at 5%, and a power (1- β) at 80%. The primary endpoint is number of new ulcers incurred.

In the general diabetic population life time prevalence of diabetic ulcers has been reported at $15-25\%^{24}$, the yearly incidence in the same group is 6%. This study focuses on patients with a deformity reported to have a 1.5 hazard ratio²⁵, and signs of an impending ulcer like callus formation, which has been reported with a relative risk of 11^{26} . The incidence of new diabetic foot ulcers incurred by the study population is set at 10%, according to the above mentioned considerations.

The incidence in the intervention group (μ_A) is set at 6%, so the anticipated reduction in incidence is 4% compared to the incidence in the control group (μ_B) which as above mentioned is set at 10%. However, the numbers for incidence of new diabetic foot ulcers is an uncertain size, especially when looking at the specific group we are looking at, therefore the standard deviation (σ) is set at 10.

The calculator used is a 2 means, 2 sample, 2-sided equality calculator. The formula is

 $nB=(1+1/\kappa) ((\sigma z1-\alpha/2+z1-\beta)/(\mu A-\mu B))2$

nB= Sample size

 κ = The matching ratio

With the above described parameters, the sample size is 98 patients, which due to an expected dropout of 10% will be extended to 110 patients.

6. **Perspective**

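### Section 5.8 plans an odds ratio for pain, but no visit after inclusion lists a pain item, so pain would probably be under-recorded after tenotomy and not comparably recorded in controls

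*Combined protocol and SAP*

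**What the plan says.** Section 5.8 introduces a short list of outcomes with "Odds-ratio will be applied to". One of them is "Pain in treated limb, associated with tenotomy", given without a scale, threshold or time point. The same section puts all data on an intention-to-treat basis. Pain is not among the secondary endpoints in section 4, which "will be complications: infections (defined as ailment associated with procedure or ulcer" and so on, followed by transfer lesions and minor and major amputations.

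On collection, section 5.5.1 has one pain entry at inclusion, "Pain associated with", placed under peripheral neuropathy in the patient history. The neurological assessment at the same visit also registers neuropathy symptoms. From Day 7 onward the visit lists carry the line "Complications associated with tenotomy is registered (if relevant". Changes to the patient's "medicine, and/or new diagnosis are registered" in both arms. Section 5.5 refers to an SOP and a MOP for how visit procedures are carried out; neither is reproduced.

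**The concern.** An outcome that is to be compared between arms needs to be asked about in both arms, in the same way and at known times. The other two odds-ratio outcomes can be traced to examination items: the ulcer evaluation includes an infection assessment, and the foot examination looks for new ulcers, which covers at least the ulcer part of transfer lesions. Pain has no such item.

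The hypothesis in section 3 is that needle tenotomy is safe as well as effective, and section 7.3 relies on a low risk of complications. Pain is a harm that only the patient can report. If it is noted only when someone judges it to be a complication of tenotomy, the tenotomy-arm rate depends on who mentions it and who writes it down, and the control arm has no matching figure. The documents describe no masking, and patients know whether they had the procedure. Once the visits have passed, the missing answers cannot be recovered.

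**Working it through.** **Step 1. Outcome against visit lists (sections 5.5.1 to 5.5.5).**

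| Visit | Pain item | Tenotomy complications line | Medicine changes / new diagnoses |
|---|---|---|---|
| Inclusion | Yes, neuropathy history only | No | Recorded as baseline history |
| Day 0 | No | No | Yes |
| Day 7 and Day 14 | No | Yes | Yes |
| Months 3, 6 and 12 | No | Yes | Yes |
| End (conditional) | No | Yes | Yes |

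The scheduled visits after inclusion number 1 (Day 0) + 2 (Days 7 and 14) + 3 (months 3, 6 and 12) = 6. A pain item appears at 0 of 6. The complications line appears at 5 of 6; the exception is Day 0, where the entry is "The allocated treatment is performed" with no complications line beside it. The visit-plan table in section 5.4 has no pain row; its nearest row is "Changes in Medicine/ new ailments". The SAE line does not help, because section 5.2 defines an SAE as death or sepsis related to the procedure.

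**Step 2. What each arm can contribute.** In the tenotomy arm, pain is recorded if staff class it as a complication. In controls the complications line does not apply, because it concerns tenotomy. Section 7.3 lets a control be offered tenotomy after an ulcer, but that patient has by then reached the ulcer endpoint. The medicine and diagnosis line covers both arms but does not ask about pain.

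**Step 3. What this does to the odds ratio.** Section 5.8 gives no figure for pain, so there is nothing to reproduce. Assume 110 patients in two equal arms, 110 / 2 = 55 each, with *x* events after tenotomy and none in controls. The raw odds ratio, *x* × 55 / ((55 − *x*) × 0), has no finite value. With 0.5 added to each cell it is (*x* + 0.5) × 55.5 / ((55 − *x* + 0.5) × 0.5):

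- *x* = 1: 1.5 × 55.5 / (54.5 × 0.5) = 3.1
- *x* = 3: 3.5 × 55.5 / (52.5 × 0.5) = 7.4
- *x* = 6: 6.5 × 55.5 / (49.5 × 0.5) = 14.6
- *x* = 11: 11.5 × 55.5 / (44.5 × 0.5) = 28.7

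These values depend on the correction and on the empty control cell. They do not compare pain between arms.

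**Step 4. Under-recording, for illustration only.** Assume a true pain rate of 20% after tenotomy (0.20 × 55 = 11 patients) and that notes on complications capture 30% to 60% of it. The recorded rate would be 0.20 × 0.30 = 6% to 0.20 × 0.60 = 12%, or 3.3 to 6.6 patients on average. Both the 20% and the capture range are assumptions; the documents support neither.

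**The case against.** The strongest reply is that the outcome is worded as pain tied to tenotomy, which makes it a procedure complication, and complications are a scheduled entry at five of the six visits. On that view there is a collection route and only the word pain is missing. The SOP or MOP may also itemise complications and ask about pain directly. Finally, pain appears once, in an analysis list, and no primary or declared secondary conclusion rests on it.

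Much of this stands, and it rules out some stronger readings that a reader might infer:

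- That there would be no pain data at all, or that pain could not be measured. The documents do not support this: complications are prompted from Day 7, so some pain would be captured. The fault is likely incomplete recording in one arm.
- That nothing about pain is known before the procedure. Inclusion records pain with neuropathy and registers neuropathy symptoms. What is missing is a value for the index foot, on a scale or in a form that a later answer could be compared with.
- That the case report form has no pain question. The form, SOP and MOP are not available, so this cannot be said; only that the protocol's visit lists do not call for one.

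The reply does not rescue the between-arm odds ratio. A complications line restricted to tenotomy gives controls no comparable measurement, however thoroughly it is completed.

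**Conclusion.** The point holds as a data-collection gap. Pain is a planned odds-ratio outcome, and 0 of 6 scheduled visits after inclusion, and not the End visit either, list a pain item. Unless the SOP or MOP supplies one, pain would probably be under-recorded in the tenotomy arm and not comparably recorded in controls, leaving the odds ratio biased or without a finite value. The visit count comes from the documents. The 55 per arm, the zero control events, the 20% rate and the 30% to 60% capture are assumptions, and the conclusion does not depend on them. Because pain is not a declared secondary endpoint, the weight is minor to moderate.

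**What to change.** Ask one identical question in both arms: pain in the index foot, yes or no, with an optional 0–10 score. Ask it at Day 0 before treatment, at Day 7 and Day 14, at months 3, 6 and 12, and at the End visit. End must be included because section 5.5.3 sends patients who develop an ulcer there, so pain answers at later visits could otherwise be missing selectively by primary outcome.

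Reword the outcome in section 5.8 as pain in the index foot, and define that foot for both arms, including patients with both feet treated, which section 5.3.1 allows for. Compute the odds ratio on the yes/no answer at one pre-stated early time point, for example Day 14, adjusted for the Day 0 answer. State how a patient whose End visit comes before that point is counted.

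If the SOP or MOP already contains such a question, stating it in the protocol and aligning section 5.8 is enough. If no question is added, drop the odds ratio and report pain descriptively as a tenotomy-arm complication.

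The cost is one extra question per visit, asked by staff already present, and a small form amendment. The question removes the difference in recording between arms; it does not remove the effect of patients knowing which treatment they had, and the report should say so.

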5.2 Patients

Inclusion criteria

- Patients aged 18 years or above
- Type 1 or 2 diabetes
- Hammer, mallet or claw toe deformity
- Impending ulcer associated with above mentioned deformities
- Able to understand written and oral information
- Ability to follow planned visits and treatment
- Able to provide informed consent in Danish and/or English

Exclusion criteria

- Revascularization procedure in the affected limb planned, or undertaken within the 4 weeks prior to screening
- Hammer, mallet and claw toe that are rigid in both MTP, IP joints
- Ulcer associated with hammer, mallet and claw toe deformities
- Toe pressure < 30mmHg
- Prior major amputations on affected or ipsilateral leg
- Other corrective operation is indicated to treat patients foot deformities as deemed by investigator
- Current treatment with cytotoxic drugs or with systemically administered glucocorticoids
- Treatment of foot ulcers with growth factors, stem cells or equivalent preparations within the 8 weeks prior to screening
- Likely inability to comply with the need for planned visits because of planned activity
- Participation in another interventional clinical foot ulcer-healing trial within the 4 weeks prior to screening
- Prior enrolment in this trial
- Judgement by the investigator that the patient does not have the capacity to understand the study procedures or provide written informed consent

Discontinuation of patients

- Patient discontinues assigned treatment for any reason, while not fulfilling one of the studies accepted endpoints
- Participants who withdraw from treatment will be asked to remain in the trial for follow-up, and data will continue to be collected and analyzed.
- Patient incurs a serious adverse event (SAE), defined as death or sepsis related to the study procedure

- Investigator decides to discontinue patient due to health or compliance reasons
- Patient misses 3 consecutive visits
- Patient misses 5 or more visits during the full treatment period

Patients who discontinue the study early will be invited to have a clinical visit before being discontinued.

Patients that are discontinued will revert to their normal treatment plan, and continue in their respective clinics.

Endpoints

- New ulcer incurred
 - When/if new ulcer is incurred pictures will be send to two external evaluators to be confirmed as new ulcer
- Patient reaches 12 month visit without incurring a new ulcer

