5.6 Randomization

- Will be done in an open source electronic data capturing system (REDCaP), using the REDCaP Randomization module. This is based on an allocation table which will be generated by a statistician at our institute, with no other connection to the study.
- Patients will be block randomized, and stratified by treatment facility. Blocks will be of 5 patients each, stratified by study site.

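### The stated 80% power for 10% versus 6% is really about 11–13%: incidences are treated as means with SD 10, and a one-arm size is used as the trial total

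*Combined protocol and SAP*

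**What the plan says.** Section 5.8 (Statistics, Sample-size) sets alpha at 5%, power at 80%, a control incidence of 10% and an intervention incidence of 6%: "so the anticipated reduction in incidence is 4% compared to the incidence in the control group". It then describes the incidence in this population as uncertain and concludes: "therefore the standard deviation (σ) is set at 10". The method is named as follows: "The calculator used is a 2 means, 2 sample, 2-sided equality calculator". The formula's output is defined only as "nB= Sample size", and the matching ratio κ is given no value. The result reads: "the sample size is 98 patients, which due to an expected dropout of 10% will be extended to 110 patients". No wording says whether these figures are per arm or in total.

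The outcome is described in two ways. Sections 4 and 5.8 call the primary endpoint a number of new ulcers. The endpoint list in section 5.2 works per patient: either a new ulcer occurs, or "Patient reaches 12 month visit without incurring a new ulcer". Section 5.6 adds: "Blocks will be of 5 patients each, stratified by study site". Section 5.8 names no test for the primary comparison.

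**The concern.** A two-means formula needs the patient-to-patient standard deviation of the outcome. The plan instead supplies a number chosen because the assumed rate is uncertain, which is a different quantity. For a yes/no outcome the SD is not free to choose, because the rate determines it. Separately, the formula returns the size of one group, and the plan seems to treat that as the whole trial.

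This is the only sample-size justification for the primary endpoint. If the true power is far below 80%, a non-significant result is the likely outcome even when the assumed benefit is real. Readers who trust the stated 80% could then conclude that needle tenotomy does not prevent ulcers.

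**Working it through.** **Inputs.** From section 5.8: two-sided α = 5% (z = 1.960), power 80% (z = 0.842), rates 10% and 6%, σ = 10, 98 patients, 10% dropout, 110 patients. Assumption: κ = 1, because no value is given and this one reproduces 98.

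**1. The plan's own figure.** n_B = (1 + 1/κ) × (σ(z₁₋α/₂ + z₁₋β)/(μ_A − μ_B))² = 2 × (10 × 2.802/4)² = 98.1. With σ on the first z term only, as the formula is printed, the result would be 2 × ((19.60 + 0.842)/4)² = 52.2. So σ was applied to both terms, and I treat the printed bracket as a text-extraction fault. For dropout, 98/0.9 = 108.9 and 99/0.9 = 110. Since n_B is one arm, two arms need about 196 patients before dropout.

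**2. One arm used as the total, keeping SD 10.** Power = Φ(4/(10√(2/n)) − 1.960).
- n = 49 per arm: Φ(4/2.020 − 1.960) = 0.51
- n = 55 per arm: Φ(4/1.907 − 1.960) = 0.55
- n = 98 per arm: 0.80

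**3. The SD.** For a yes/no outcome, √(0.10 × 0.90) = 0.300 and √(0.06 × 0.94) = 0.237, that is 30.0 and 23.7 points. An SD of 10 points would correspond to a rate of about 1% (√(0.01 × 0.99) = 0.0995). A Poisson count with mean 0.10 has SD √0.10 = 0.316, so reading the endpoint as a number of ulcers does not rescue the figure.

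**4. Power for 10% versus 6%.** Normal approximation: Φ((0.04 − 1.960 × SE₀)/SE₁), with SE₀ = √(2 × 0.08 × 0.92/n) and SE₁ = √((0.0900 + 0.0564)/n). At n = 55: Φ((0.04 − 1.960 × 0.0517)/0.0516) = Φ(−1.19) = 0.117. The exact columns sum the binomial probabilities of all result pairs that reject.

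| Per arm | Reading of the plan | Normal approx. | Exact chi-square | Fisher |
|---|---|---|---|---|
| 49 | 98 in total | 10.9% | 12.8% | 4.2% |
| 55 | 110 in total | 11.7% | 11.5% | 5.1% |
| 98 | 98 per arm | 17.6% | 17.8% | 11.7% |
| 110 | 110 per arm | 19.2% | 19.9% | 13.4% |

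Blocks of 5 cannot split 1:1. A 3:2 split of 110 gives 9.5% by chi-square and 8.1% by Fisher with 66 controls and 44 tenotomies, and 13.8% and 8.8% with the arms reversed.

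**5. Expected events.** 49 × (0.10 + 0.06) = 7.8; 55 × 0.16 = 8.8.

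**6. Size needed for 80%.** (1.960√(2 × 0.08 × 0.92) + 0.842√0.1464)²/0.04² = 721 per arm. For Poisson counts: 2.802² × 0.16/0.0016 = 785 per arm. For time to first ulcer, HR = ln 0.94/ln 0.90 = 0.587, so events needed = 4 × 2.802²/(ln 0.587)² = 111. With 7.8 to 8.8 events, power is 11–12%.

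**7. Other control rates.** Holding the relative reduction at 40% with 55 per arm, exact chi-square power is 11% at a control rate of 10%, 21% at 20%, 31% at 30%, 58% at 50% and 84% at 70%. It crosses 80% at about 67%. Larger effects are detectable at lower rates: 20% versus 3.7% and 30% versus 9.5% each have about 80% power by chi-square, but 69% and 71% by Fisher. Even 10% versus 0% has 81% by chi-square and only 48% by Fisher.

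**The case against.** The strongest reply is that the plan never says 98 or 110 is the total. If it was meant per arm, the plan's own means model does reach 80%, and about 16 to 18 events would be expected (98 × 0.16 = 15.7; 110 × 0.16 = 17.6). This is fair: the total is the natural reading of an unqualified number of patients, not an explicit statement. It does not save the claim, because the SD error alone holds power below 20%.

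A second reply is that the true control rate may exceed 10%. Section 5.8 itself cites a hazard ratio of 1.5 for the deformity and a relative risk of 11 for callus. That is possible, but the plan commits to 10% and claims 80% there. The 67% crossing point depends on my choice of a fixed 40% relative reduction; the plan states its effect as an absolute 4 points.

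Three qualifications stand.
- With no test named, 11–13% is the normal-approximation and chi-square figure, and Fisher gives 4–5%. The 12.8% at 49 per arm is slightly flattered, because the uncorrected chi-square test there has a true type I error of 6.1% at a common rate of 8%.
- The rows for 55 and 110 per arm assume no dropout. With 98 evaluable patients in total, the 49-per-arm row applies.
- The missing κ, the block size and the unnamed test are separate omissions. They do not cause the power error, but they prevent a single exact figure.

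**Conclusion.** The concern holds. The stated 80% power is wrong on every reading of section 5.8. Taking 98 to 110 as the total, with 1:1 allocation and a two-sided 5% test, power for 10% versus 6% is 10.9–12.8% by normal approximation or chi-square and 4–5% by Fisher. If the assumed effect is real, the chance of a non-significant result is therefore about 87–89% by chi-square and about 95% by Fisher. The wrong SD is the larger error: alone it reduces power to 18–19%. Using one arm's size as the total would alone reduce it to 51–55%. The conclusion does not depend on whether the outcome is analysed as a proportion, a count or a time to first ulcer. This must be corrected before the results are interpreted.

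**What to change.** Rewrite the sample-size paragraph in section 5.8, leaving enrolment as planned:
- Replace the two-means calculation with one for two proportions, or for time to first ulcer, matching the primary analysis.
- Name the primary test, state the allocation ratio and align it with the block size in section 5.6, and say whether each number is per arm or total.
- State what 110 patients deliver: about 12% power for 10% versus 6% by normal approximation or chi-square (about 5% by Fisher), the reduction detectable with 80% power under the named test, and power over the plausible range of control rates.
- Commit to reporting the primary comparison with a 95% confidence interval, so that a non-significant result is not read as no effect. For a risk difference the expected half-width is 1.96 × √(0.1464/55) = 10.1 points, or 10.7 points at 49 per arm, against an assumed effect of 4.

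The cost is rewording and a short recalculation, with no extra patients. The drawback is that the plan must openly state a much lower power.
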